### 7.2.2 Exclusion Criteria

A flow diagram to highlight the exclusion criteria is shown in [Figure 2](#) below.

- Children whose mother immigrated to Sweden, Denmark, or Norway both after 2006 and after age 9 years will be excluded as vaccination exposure status is unknown.
- Since the hypothesis of HPV transmission is that it occurs in mothers giving birth to biological children, adopted children will be excluded from the analysis as vaccination status of the actual, biological mother will be missing.
- Children whose mother received the bivalent vaccine Cervarix will be excluded since it provides no effectiveness against the causative HPV types (6 and 11) in RRP.
- Any child (case or control subject) who previously received any HPV vaccine will be excluded from analysis.

[figure not shown]

Figure 2 Flow Diagram Describing Steps to be Used in Creation of Data Set for Each Country, Based on Listed Inclusion/Exclusion Criteria

PRODUCT: V501/V503	PROTOCOL/AMENDMENT VERSION NO.: V503-095-00-v3
REVOPS ID NO: NIS102781	CORE DRC APPROVAL DATE: 18MAR2024
EPIDEMIOLOGY NO.(PE STUDIES ONLY): 08039.022	

### 7.2.3 Stratification

Stratified analyses, statistical adjustment, and/or assessment of interaction will be performed for the primary objective according to the following factors:

- 1) Age at vaccination of mother (before 17 years of age vs 17 years or older)
- 2) Time since vaccination of mother ( $\leq 10$  years vs  $> 10$  years)
- 3) Maternal history of external genital warts prior to delivery (yes/no)

### 7.3 Variables

All the below variables are intended to be analyzed as categorical variables. Where applicable, continuous covariates such as income or number of years of education, will be categorized into standard categories.

Validation: Primary analyses will be carried out using the ICD-10 code D14.1 (benign tumor of the larynx), and if needed, the equivalent codes to D14.1 in the predecessor ICD system ICD-9 and ICD-7. In countries where available/complete from the pathology/cancer registry, appropriate topography/morphology codes (identified in consultation with sub-specialist clinical experts) will also be used to increase specificity of the outcome definition in primary analyses. There will be no medical chart review; however, descriptive statistics of the combinations of diagnostic and procedural codes for all the cases in the dataset will be provided. Study investigators will further work with local clinician expert(s) as needed, to investigate and define which combination of procedural codes (e.g., DQB10, UDQ25 and UDW22) for RRP may provide further specificity to validate the outcome. The plan is to perform this procedure for all cases identified.

Otorhinolaryngologists/phoniatricians as well as other experts in RRP, HPV, epidemiology, and biostatistics external to the study have provided valuable input on the study design including advising on use of ICD-10 code D14.1 and will continue to be consulted as needed throughout the study. A Scientific Review Committee with expertise in RRP, HPV, epidemiology, and biostatistics will be formed to provide an independent review of study findings, including interpretation of results.

#### 7.3.1 Exposure

A subject's mother will be defined as fully vaccinated if she has received 2 or 3 doses (depending on age group-specific dose regimen recommendation) of HPV vaccine with GARDASIL or GARDASIL 9. Among individuals who initiated vaccination prior to 15 years of age, receipt of 2 doses administered at 0 and 6-12 months is considered fully vaccinated, whereas among individuals who initiate vaccination after 15 years of age, 3 doses administered at 0, 2, and 6 months is considered fully vaccinated. Sensitivity analysis will also be performed where individuals will be classified as exposed/vaccinated if they received

PRODUCT: V501/V503	PROTOCOL/AMENDMENT VERSION NO.: V503-095-00-v3
REVOPS ID NO: NIS102781	CORE DRC APPROVAL DATE: 18MAR2024
EPIDEMIOLOGY NO.(PE STUDIES ONLY): 08039.022	

at least one vaccine dose, according to age at vaccination (<17 years vs.  $\geq 17$  years), and time since vaccination ( $\leq 10$  years vs. >10 years). While higher effectiveness may be expected among females vaccinated as children (e.g., <14 years), few cases of JoRRP have occurred among children born to mothers from 1992+ birth cohorts (i.e., vaccinated at age 13 in 2007 or later), which may be expected considering that the average maternal age at birth of first child is  $\sim 29$  years in Nordic countries.

### 7.3.2 Outcomes

Health outcomes are defined as clinical events or outcomes which may be represented as diagnoses, treatment or procedures.

Definition of cases:

- A subject will be defined as having JoRRP if he/she has  $\geq 1$  hospitalization or outpatient record with diagnosis registered as D14.1, with appropriate topography/morphology codes (where possible to obtain from pathology/cancer registry), between 0-9 years of age [29].

Selection of controls: random selection of up to 100 controls per case from the underlying population at risk, using incidence density sampling procedures. Matching criteria will be age of mother (+/- 1 year), sex of child, calendar year of case diagnosis, and region where case was diagnosed.

### 7.3.3 Covariates

In an observational study, where exposure is not randomized, it is important to explicitly express which association is being investigated, and *a priori* explain which covariates are proposed for adjustment and why. To this end, a Supplement to this Protocol has been prepared which lists in detail subject matter expertise reasoning and motivation regarding potential confounders. Therein, a closer discussion on variables of consideration, the size of associations when known, and potential causal mechanisms supporting a confounding theory are discussed (Annex 1).

Covariates (potential confounders and/or effect modifiers):

- An individual (mother) will be defined as having EGW based on  $\geq 1$  hospitalization or outpatient record, and/or a prescription for a pharmaceutical against anogenital warts as validated in studies performed in the Nordic region [32] [33].
- Method of delivery (vaginal versus cesarean section). Evidence is inconsistent regarding whether birth by cesarean section is protective against JoRRP [14].
- Education level of mother (highest level achieved) will be categorized as low/medium/high according to the Swedish, Danish, and Norwegian system of number of school years.

PRODUCT: V501/V503	PROTOCOL/AMENDMENT VERSION NO.: V503-095-00-v3
REVOPS ID NO: NIS102781	CORE DRC APPROVAL DATE: 18MAR2024
EPIDEMIOLOGY NO.(PE STUDIES ONLY): 08039.022	

- Smoking status of the mother at first prenatal visit will be assessed (yes/no).
- Annual family income will be categorized in tertiles or quantiles relative to the general female population of Sweden, Denmark, and Norway of corresponding age structure.
- Mother's country of birth (Sweden/Norway/Denmark or other).

Missing data for covariates will be included as variable categories marked "Missing" and will be included as separate categories in the statistical analysis.

#### 7.4 Data Sources

The study will be conducted using only structured secondary data.

Data sources for this study include for **Denmark** the following population, patient, and vaccine registries:

##### Central Population Registry

- date of birth (subject/mother)
- gender
- migration status (subject/mother)
- date of death, if applicable

##### National Patient Registry

- diagnosis of JoRRP
- date of diagnosis
- diagnosis of external genital warts (maternal)
- diagnosis of AoRRP (maternal)

##### Pregnancy/Birth Registry

- mode of delivery (vaginal or caesarean section)
- smoking status of the mother during index pregnancy (1st antenatal visit)

##### Prescription Registry (covers women vaccinated outside program)

- type of HPV vaccine (dates of administration)
- number of doses
- dates of administration
- genital warts treatment (Podyphyllotoxin)
- date(s) of diagnosis

PRODUCT: V501/V503	PROTOCOL/AMENDMENT VERSION NO.: V503-095-00-v3
REVOPS ID NO: NIS102781 EPIDEMIOLOGY NO.(PE STUDIES ONLY): 08039.022	CORE DRC APPROVAL DATE: 18MAR2024

The National Health Insurance Service Registry (covers girls/women vaccinated free of charge)

- type of HPV vaccine received
- number of doses
- date(s) of administration

#### Family database

- index data for linking to mothers of cases and controls in the primary objective to obtain relevant maternal information

#### Statistics Denmark

- education level of mother
- household/family income

#### Pathology Register

- topography/SNOMED codes in relation to RRP

Data sources for this study include for **Sweden** the following population, patient, and vaccine registries:

#### Total Population Registry

- date of birth (subject/mother)
- gender
- migration status (subject/mother)
- date of death, if applicable

#### National Patient Registry

- diagnosis of JoRRP
- date of diagnosis
- diagnosis of external genital warts (maternal)
- diagnosis of AoRRP (maternal)

#### Medical Birth Registry

- mode of delivery (vaginal or caesarean section)
- smoking status of the mother during index pregnancy (1st antenatal visit)

PRODUCT: V501/V503	PROTOCOL/AMENDMENT VERSION NO.: V503-095-00-v3
REVOPS ID NO: NIS102781	CORE DRC APPROVAL DATE: 18MAR2024
EPIDEMIOLOGY NO.(PE STUDIES ONLY): 08039.022	

Prescribed drug Registry (covers women vaccinated outside program)

- type of HPV vaccine (dates of administration)
- no. of doses
- dates of administration
- genital warts treatment (Podyphyllotoxin)

SVEVAC/National Vaccination Registry (covers girls/women vaccinated free of charge)

- type of HPV vaccine received
- no. of doses
- date(s) of administration

Multi-generation registry

- index data for linking to mothers of cases and controls in the primary objective to obtain relevant maternal information

LISA (Swedish Longitudinal integrated database for health insurance and labour market studies)

- education level of mother
- household/family income

Data sources for this study include for **Norway** the following population, patient, and vaccine registries:

The National Population Registry of Norway (“Folkeregisteret”)

- date of birth (subject/mother)
- gender
- migration status
- date of death, if applicable
- index data for linking to mothers of cases and controls in the primary objective to obtain relevant maternal information

The National Patient Registry in Norway (NPR)

- diagnosis of JoRRP (date of diagnosis)
- diagnosis of external genital warts (maternal) (date(s) of diagnosis)
- diagnosis of AoRRP (maternal)

The Medical Birth Registry of Norway (MBRN)

- mode of delivery (vaginal or caesarean section)
- smoking status of the mother during index pregnancy (1st antenatal visit)

PRODUCT: V501/V503	PROTOCOL/AMENDMENT VERSION NO.: V503-095-00-v3
REVOPS ID NO: NIS102781	CORE DRC APPROVAL DATE: 18MAR2024
EPIDEMIOLOGY NO.(PE STUDIES ONLY): 08039.022	

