### Norwegian Prescribed Drug Registry

- Prescription(s) for HPV vaccine (type of vaccine)
- Prescription(s) for genital warts treatment (maternal) (Podophyllotoxin, Imiquimod, Sinecathecins)
- Date(s) of prescription(s)

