## 7.8 Data Analysis

### 7.8.1 Statistical Methods

Conditional logistic regression will be used for estimation of odds ratios (ORs) and corresponding 95% confidence intervals in the pooled analysis using 1-step approach, with adjustment for clustering and adjustment for relevant covariates; all measured with similar high accuracy in each country. Children whose mother received the bivalent vaccine, even in combination with GARDASIL or GARDASIL 9, will be excluded from the analysis. Similarly, in the primary analysis, children whose mother had history of genital warts prior to vaccination will be excluded as vaccination is exclusively prophylactic, i.e., there is no therapeutic effect against HPV infection or related disease.

Each case subject and his/her controls constitute a risk stratum, or a risk set matched on age of mother, sex of child, and region where case was diagnosed. The distribution of these factors is therefore equalized in the model by design, which removes the need for adjusting for these factors so long as the risk strata are retained. Regarding mode of delivery, history of maternal genital warts, maternal smoking status, education level and income, it was decided not to match on these factors, as they may be of interest to study as confounders or effect modifiers.

When the outcome of a study is rare, which is the case for JoRRP, the OR approximates the risk ratio (or relative risk, RR) [35]. Further, incidence density sampling (i.e. random sampling of controls from the available population still at-risk at the particular point in time of the case's diagnosis) also ensures that ORs are a direct estimate of the hazard ratio, again interpretable as the risk ratio in our study [36]. ORs obtained through the conditional logistic regression model will therefore be interpreted as the corresponding RR.

It is expected that use of ICD-10 code D14.1 will be highly accurate for diagnosis of RRP; however, where possible, effort will be made to further increase specificity, applying appropriate topography/morphology codes. We also plan to perform sensitivity analyses restricted to RRP cases with related diagnostic or other treatment procedures, and/or subcode D14.1.A, as described above.

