#### 4. Maternal history of genital warts

The lead risk factor for JoRRP is a maternal history of genital warts. Most children who develop RRP are born to mothers with genital warts [55]. In the same Danish retrospective cohort study cited above, children born to mothers with history of genital warts were found to have ~230-fold increased risk of JoRRP compared to children born to mothers without history of genital warts (RR=231.4, 95% CI=135.3-395.9) [4]. Investigators also reported that longer delivery ( $\geq 10$  hours versus  $< 10$  hours) was associated with a two-fold greater risk of JoRRP (RR=2.0, 95% CI=1.1-3.5), which suggests vertical transmission of HPV infection during delivery [4].

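### Maternal genital warts are to be found through one drug in Denmark and Sweden but three in Norway, under a single definition that names no drug

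*Protocol*

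**What the plan says.** Section 7.3.3 gives one rule for all three countries. A mother has EGW if she has at least one "hospitalization or outpatient record, and/or a prescription for a pharmaceutical against anogenital warts as validated in studies performed in the Nordic region". No drug is named.

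Section 7.4 then lists what each country takes from its registries:

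- **Diagnoses.** All three take them from the National Patient Registry: "diagnosis of external genital warts (maternal") in Denmark and Sweden, and "diagnosis of external genital warts (maternal) (date(s) of diagnosis") in Norway.
- **Prescriptions, Denmark (Prescription Registry) and Sweden (Prescribed drug Registry).** "genital warts treatment (Podyphyllotoxin"), with no other drug and no sign that it is an example.
- **Prescriptions, Norway (Norwegian Prescribed Drug Registry).** "Prescription(s) for genital warts treatment (maternal) (Podophyllotoxin, Imiquimod, Sinecathecins").

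The variable has several uses. Under 7.8.1, "children whose mother had history of genital warts prior to vaccination will be excluded as vaccination is exclusively prophylactic", and footnote 4 of Table 3 builds this into the exposed group. Section 7.2.3 makes EGW history before delivery a yes/no stratifier. Section 6.2 puts it first among the risk factors to be explored. Annex 1 states: "The lead risk factor for JoRRP is a maternal history of genital warts".

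Section 7.8.1 describes a one-step pooled analysis and says that the covariates are measured with comparably high accuracy in each country. Section 7.10 concedes that some variables differ between registers and will be adapted through a common data model.

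**The concern.** The definition and the source lists do not agree, and no reason is given for the difference. A mother whose warts are known only from a prescription for imiquimod or sinecatechins is EGW-positive in Norway and EGW-negative in Denmark and Sweden, yet the three datasets are pooled as if they held one variable.

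Three things are at stake:

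1. **The primary exclusion.** Vaccinated mothers with earlier warts who are not recognised stay in the vaccinated group. Annex 1 expects women with previous warts to be somewhat more likely to seek vaccination, so this group need not be negligible.
2. **The EGW strata.** Section 7.8.2 would read effectiveness among children of EGW-positive mothers as evidence that vaccination also blocks mother-to-child transfer. That reading needs strata that mean the same thing in each country.
3. **The exploratory EGW odds ratio.** Missed positives in the reference group lower it.

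**Working it through.** **Reach.** Section 7.5 expects about 100, 50 and 50 cases in Sweden, Denmark and Norway. The sum is 200, as stated. Sweden and Denmark together hold (100 + 50)/200 = 75%.

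**Who can be missed.** A diagnosis record counts in every country. The gap is therefore confined to Danish and Swedish mothers with (a) a prescription only for an unlisted drug and (b) no hospital or outpatient record. Call their share of all affected mothers *m*. The documents give no value for it; 10% and 20% are used below as assumptions.

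**Contamination of the EGW-negative stratum in Denmark and Sweden.** Let *f* be the share of cases whose mother truly has EGW. With perfect specificity and *m* the same for cases and controls, the share of EGW-negative cases with a truly affected mother is

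share = *m f* / (*m f* + 1 − *f*).

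The protocol points to two very different values of *f*.

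*Lower.* The Australian surveillance study described in Section 5 found a maternal history of warts in 20% of 15 cases, so *f* = 0.20.

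- *m* = 0.10: 0.02/(0.02 + 0.80) = 2.4%
- *m* = 0.20: 0.04/(0.04 + 0.80) = 4.8%

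*Higher.* Annex 1 cites a relative risk of 231.4. With an assumed EGW prevalence of 1% among mothers, *f* = 0.01 × 231.4/(0.01 × 231.4 + 0.99) = 2.314/3.304 = 70%, in line with the Annex 1 remark that most affected children have mothers with warts.

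- *m* = 0.10: 0.2314/(0.2314 + 0.99) = 19%
- *m* = 0.20: 0.4628/(0.4628 + 0.99) = 32%

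The prevalence assumption also matters at this relative risk. At 0.5% with *m* = 0.10 the share is 0.1157/(0.1157 + 0.995) = 10%; at 2% with *m* = 0.20 it is 0.9256/(0.9256 + 0.98) = 49%.

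**Pooled over the three countries.** If affected mothers are spread like the cases and Norway misses none by this route, the pooled missed share is 0.75 × *m*, that is 7.5% or 15%. The pooled contamination is then:

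- *f* = 0.20: 0.015/0.815 = 1.8% and 0.030/0.830 = 3.6%
- 1% prevalence with relative risk 231.4: 0.1736/1.1636 = 15% and 0.3471/1.3371 = 26%

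**Effect on the EGW relative risk in Denmark and Sweden (higher scenario).** Apparent RR = 231.4 ÷ [(*m* × 2.314 + 0.99)/(*m* × 0.01 + 0.99)].

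- *m* = 0.10: 231.4/(1.2214/0.991) = 188
- *m* = 0.20: 231.4/(1.4528/0.992) = 158

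**Direction for the primary odds ratio.** The exclusion turns on warts before vaccination, so as worded it acts on vaccinated mothers. Missing some of them leaves higher-risk women in the vaccinated group. Compared with the analysis the plan intends, this moves the estimate toward no effect. Its size cannot be computed from the documents.

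**The case against.** Section 7.4 can be read as a summary. Section 7.6 leaves the exact variable lists to the Swedish data orders and to a Danish data management plan, and 7.10 promises a common data model. The definition in 7.3.3 is also tied to validation in Nordic studies, so the narrower list might be a validated national algorithm. This has some force, but 7.4 names specific drugs and names them differently by country. A common data model cannot recover prescriptions that were never ordered; it could only bring Norway down to one drug, which is narrower than 7.3.3.

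Three stronger readings are tempting and are not supported:

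- *That affected mothers are shown to be missed in the two countries with most cases.* Denmark and Norway are each put at about 50 cases, and a patient-registry diagnosis counts everywhere. A loss is possible; its size is unknown.
- *That about a fifth to a third of EGW-negative cases are contaminated.* This needs about 70% of cases to have affected mothers. The 20% figure in Section 5 gives 2-5%. The title of the study behind the relative risk also concerns warts in pregnancy, whereas the plan uses any history before delivery.
- *That the primary odds ratio is confounded by country.* Risk sets are matched on region and so lie within one country, and EGW is not among the adjustment factors in Table 3. Note 2 to Table 3 also plans a table irrespective of EGW history, which this misclassification does not touch.

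The remedy has a cost too. Data collection began in March 2023, so orders may need amending. An added drug may also have been prescribed for something else: at 1% prevalence, false positives in 0.2% of unaffected mothers would equal 0.002 × 0.99/0.01, or about 20%, of the true positives.

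**Conclusion.** The inconsistency is real and should be corrected. One definition in 7.3.3 is served by two different drug lists in 7.4, so the statement of comparable accuracy in 7.8.1 is not supported for EGW. The consequences are a less complete exclusion in Denmark and Sweden, probably conservative for effectiveness, and pooled EGW strata and an exploratory EGW odds ratio that mix two measures.

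The number of mothers affected is not in the documents. The range of about 2-5% to 19-32% within Denmark and Sweden rests on an assumed 10-20% missed and on which of the protocol's two pictures of EGW among mothers of cases applies. The discrepancy in the text does not depend on those figures. Nothing here shows material damage to the primary odds ratio.

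**What to change.** 1. In 7.4, list podophyllotoxin, imiquimod and sinecatechins for the Danish and Swedish prescription registries, as for Norway.
2. In 7.3.3, name that one list as the prescription part of the EGW definition in all three countries.
3. Add a sensitivity analysis that defines EGW by podophyllotoxin only, or by diagnosis records only, in all three countries.
4. If the extra data cannot be obtained, state the difference and its reason, and qualify the accuracy statement in 7.8.1.

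The cost is two more drugs in orders to registries already being linked, possibly as amended orders, plus one additional run. Specificity may fall where a drug was prescribed for another condition; comparing the main and sensitivity results would show whether that matters.

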### Norwegian Cancer Registry

- Norpat codes on morphology/topography to increase specificity of RRP diagnosis (if feasible)

### Norwegian Prescribed Drug Registry

- Prescription(s) for HPV vaccine (type of vaccine)
- Prescription(s) for genital warts treatment (maternal) (Podophyllotoxin, Imiquimod, Sinecathecins)
- Date(s) of prescription(s)

### The Norwegian Immunization Registry (SYSVAK)

- type of vaccine received
- date(s) of administration

### Statistics Norway (SSB)

- education level of mother
- household/family income

## 7.4.1 Study Procedures

The proposed study is non-interventional in nature and does not entail any risk to the study participants, apart from the possibility of integrity breach through accessing public records. Therefore, it must be subject to approval from the ethics review committees in each of the respective countries to mandate this access. All study investigators/research institutions have substantial experience in handling similar studies in an integrity-assured manner and numerous safeguards are in place to maintain confidentiality of information on the study subjects. Also, all data are pseudonymized and the researcher does not have access to the underlying identifiers as these are protected separately by the data holder authority.

